### **Medicaid Health Homes and Diabetes Management**

HH-eligible patients with diabetes are likely to be an especially vulnerable population, and one where disparities in access and quality are starker. The prevalence of diabetes among patients with serious

mental illness (SMI) is higher than in the general population. Increased mortality among those with SMI is partially attributable to higher rates of cardio-metabolic disease.(23, 24) Patients with SMI and diabetes have been found to be less likely to receive indicated services and care, and more likely to be admitted to the hospital with ambulatory-care sensitive conditions when compared to those without SMI.(23, 25) Over half of patients with diabetes have at least one other chronic condition, and a large proportion of these have two or more.(26, 27) Suffering from multiple chronic diseases puts individuals at greater risk of preventable hospitalizations, poor functional status, higher cost care, and increased mortality.(26, 28)

HH enrollment would ideally improve the processes and the outcomes of care; and it would reduce health disparities (related to the process and outcomes of care) for individuals with diabetes. Through coordination of care, intensive case management, and attention to social needs, individuals with diabetes could develop better disease self-management, receive proper specialist evaluation and evidence-based regimens, and work with a team that identifies opportunities to bolster social support. As the HH intervention is applied differently at different facilities, these effects may vary across institutions. In NYS, evaluations are currently being conducted of the overall HHs program and of those participants with substance use disorders and those with HIV; however, by focusing on individuals with diabetes, the proposed research would add substantially to knowledge about the effect of HHs on patients on an important common chronic condition, diabetes.

#### **Impact of COVID-19 on Medicaid Health Homes**

In spring 2020, New York City (NYC) was the American epicenter of the COVID-19 pandemic. In addition to direct health effects, the pandemic also had major impacts on the delivery of health care and social services. Low-income patients with diabetes, especially among racial/ethnic minorities, are more vulnerable to the serious morbidity and mortality associated with COVID-19; and, they are more likely to experience a lack of access to health care and social services. Outpatient medical care essentially shut down for in-person visits during the pandemic, and access to primary care, disease management, and medications continue to be disrupted. Limited mobility and social determinants, such as access to transportation, employment, internet connectivity, and competing needs, also likely impacted access to health care and social services and clinical outcomes during the pandemic. In response, New York State (NYS) Medicaid adapted regulations to allow Health Homes (HHs) to bill for remote delivery of care management services. As a result, HH participants are likely to have higher rates of health care and social service utilization and better health outcomes, compared to similar HH non-participants.

The proposed study will be among the first to utilize the New York City Clinical Data Research Network (NYC-CDRN) data and infrastructure to examine the effects of a population-level health policy, the implementation of the Medicaid HH program, on the process, outcomes, and disparities of care for a common chronic condition, diabetes.

#### **3) Setting of the Human Research**

The primary research team is located at the Icahn School of Medicine at Mount Sinai. Other members of the team are located at Weill Cornell Medicine and the New York Academy of Medicine (NYAM) (Co-PI [name]). NYAM is a non-profit center of interdisciplinary research, evaluation, policy, and

program initiatives focused on urban health. The study is a collaboration with the New York City Clinical Data Research Network and the HEAL at NYU School of Medicine.

The New York City Clinical Data Research Network (NYC-CDRN) was founded with support from the Patient-Centered Outcomes Research Institute (PCORI) to join its PCORnet program. The mission of the NYC-CDRN is to create an accessible, sustainable, scalable clinical data network to facilitate patient-centered research, learning healthcare systems and a national research network (PCORnet). Efforts are focused on five goals:

1. Creating thoughtful privacy policies that protect the identities of individual patients, clinicians, and health systems;
2. Establishing a de-identified database with clinical data on at least one million New Yorkers;
3. Engaging patients, caregivers, and clinicians in network governance and decision-making;
4. Embedding research activities in the delivery of healthcare to minimize the burden on patients, clinicians, and health systems; and
5. Developing a high-functioning, sustainable governance structure.

NYC-CDRN's program builds on the joint efforts of 22 organizations – including academic medical centers, associated Clinical and Translational Science Centers, federally qualified health centers, regional health information organizations (RHIOs), research institutions, consumer advocacy groups and government agencies - to develop a patient-centered, sustainable network for conducting research across New York City and the nation and facilitating a learning healthcare system.

The Health Evaluation and Analytics Lab (HEAL) promotes applied research to help health sector organizations evaluate initiatives that seek to improve health outcomes among populations and to improve health care delivery practices. HEAL has built a unique New York State Medicaid claims file. This large data system allows for a wide range of evaluative work focused on improving care and outcomes for the most vulnerable New Yorkers, who rely on Medicaid to pay for their medical care needs. The data set also allows providers to better track the services received by their patients. The effort to create the claims file analytical system was financially supported by the New York State Health Foundation and was done in close collaboration with the New York State Department of Health.

Participating organizations include:\*

**Figure 1: NYC-CDRN Organizational Structure**

#### **4) Resources Available to Conduct the Human Research**

Our study team includes multiple experienced investigators, a data analyst, experienced project management staff, and an experienced engagement manager. This team has the knowledge and resources needed to conduct the retrospective cohort analysis, focus groups, and HH leader interviews. ISMMS has robust data management and security protocols in place to safely store study data. For this study, we will be working with the NYC-CDRN, which, as described above, has the resources to combine data from multiple institutions and facilitate collaboration, and to ensure data security and quality.

**Activity 2:** The primary team at ISMMS will collaborate with partner institutions to conduct interviews. Investigators and stakeholders from the partner institutions will advise the primary team on reaching out to clinical providers, care management agencies, and HHs about contacting their patients. The primary team will reach out to and follow up with these providers. Then, the primary team will reach out to eligible participants. The primary team will conduct all interviews.

#### **5) Study Design**

##### **a) Recruitment Methods**

**Activity 1:** For this retrospective data analysis, we will not be recruiting any participants. The study will rely upon a distributed query of the participating healthcare systems in the NYC-CDRN. For a full description of query design, see section f for Activity 1. The protocol relies upon the NYC-CDRN infrastructure established under the BRANY IRB-approved protocol #14-02-95-380 (PI: [name]) to accomplish the data aggregation.

**Activity 2:**

Health Home patients will be recruited through referral from HH care managers. Care managers will share a flyer (created by the study team) describing the study with patients. If patients are interested, the care manager will add their contact information to an excel spreadsheet that will be shared with study staff. Study staff will follow up via phone. If the participant is reached via phone and interested in participating, study staff will provide further information about the interview process and content and will schedule the phone/virtual interview.

**Activity 3:** In order to identify leaders from HHs in NYC, we will utilize multiple sources including internet sites for each HH listing name and contact information for those in leadership positions, referrals from our Patient and Stakeholder Advisory Board (of which one member is a leader of a NYC HH and thus familiar with many of these individuals), from interviewees who have already participated, and HH forums. Study staff will reach out to individuals by phone or email and describe the study. If potential participants are interested, the study staff member will set up a telephone or video meeting, during which verbal consent will be obtained prior to any data collection.

Health Home directors that are study stakeholders and partners will assist with the identification of HH care managers and will share contact information of interested participants with the study staff in an excel spreadsheet. Study staff will follow up via email or via phone. If the participant is reached and interested in participating, study staff will provide further information about the interview process and content and will schedule the phone/virtual interview.

**Activity 4:** For this retrospective data analysis, we will not be recruiting any participants. We plan to use NYS Medicaid administrative and claims data in the Medicaid Data Warehouse, available to researchers at HEAL at New York University.

**b) Inclusion and Exclusion Criteria**

**Activity 1:** For this analysis, the study cohort will consist of patients who: 1) have Type II diabetes, 2) are insured by Medicaid, and 3) are either part of a Health Home or meet criteria for Health Home enrollment, but are not enrolled in a Health Home.

1) In consultation with the Diabetes Subcommittee of the NYC-CDRN, this protocol will use the SUPREME-DM definition of diabetes, which has been previously validated.(29) This definition has been adopted as a standard across the three CDRNs that have diabetes as a disease focus (New York, Louisiana, and Oregon-Advance). It consists of the following algorithm (see Table 1), where any of the listed criteria are sufficient for inclusion for any patient with at least one outpatient visit at a participating CDRN site within the past year.

Table 1. Diabetes Definition	
Criteria	Parameter
ICD9/10 - Inpatient discharge diagnosis	1 or more of (250.x, 357.2, 366.41, 362.01–362.07)
ICD9/10 - Outpatient diagnosis	2 or more of (250.x, 357.2, 366.41, 362.01–362.07) Visits must occur on separate days. Ambulatory visits only.

HbA1c	2 or more HbA1c's at >=6.5%	Tests must be on separate days no more than 2 years apart.
Fasting Plasma Glucose	2 or more at >= 126 mg/dL	Tests must be on separate days no more than 2 years apart.
Random Plasma Glucose	2 or more at >= 200 mg/dL	Tests must be on separate days no more than 2 years apart.
Random plasma plus fasting glucose	1 at >= 200 mg/dL AND 1 at >= 126 mg/dL	Tests must be on separate days no more than 2 years apart.
HbA1c plus fasting glucose	1 at >= 6.5% and 1 at >= 126 mg/dL	Tests can occur on same day but cannot be more than 2 years apart.
HbA1c plus random plasma glucose	1 at >= 6.5% and 1 at >= 200 mg/dL	Tests can occur on same day but cannot be more than 2 years apart.
2-h 75-g OGTT	1 at >= 200 mg/dL	Do NOT count if measured during pregnancy.
Medications	Sulfonylurea, insulin, biguanide, SGLT-2 inhibitors, thiazolidinedione, alpha-glucosidase inhibitor, incretin mimetic, meglitinide, amylin analog, or dipeptidyl peptidase inhibitor	>= 1 prescription. If dispense was for metformin, any thiazolidinedione, or exenatide, at least one lab test (HbA1c > 6.5%, random glucose >= 200 mg/dL, fasting glucose >= 126 mg/dL) is also required.

2) In order to be eligible for the cohort, subjects need to have been insured by Medicaid at some point during the years 2010-2016. This categorization will be available in the NYC-CDRN data set. Data will be gathered only from individuals who meet criteria for diabetes and have been insured by Medicaid.

3) Subjects who have participated in the HH program will be the treatment group in this study. Medicaid data contains a field that will identify those patients who were a part of this program during the study period. Our comparison group will consist of similar individuals who were not part of the HH program. The comparison group will be constructed of patients who have been propensity score matched to those in the treatment group, and are therefore similar on a number of characteristics.

**Activity 2:** For the focus group and interview aspect of this study, we will be conducting 2 rounds of data collection, in years 2 and 5. We aim to recruit 20-40 participants in year 5. Year 5 data collection will consist of only individual interviews. Inclusion criteria are as follows:

- a. English-speaking
- b. Are enrolled in a HH
- c. 18 years old or older

All participants must be able to provide informed consent to participate, and must be able to speak with a study staff member over the phone/video call. All individuals must be able to communicate in English.

The ISMMS study team will coordinate with stakeholders who lead NYC HHs to engage HH members/patients who are potential participants.

**Activity 3: HH leaders:** In order to participate in this portion of the study, individuals must speak English and be in a leadership position at a HH entity in NYC or a NYC HH-affiliated Care Management Agency (CMA). Other than not meeting the inclusion criteria, there are no exclusion criteria.

**Care managers:** In order to participate in this portion of the study, individuals must speak English and be in care manager position with a NYC HH-affiliated Care Management Agency (CMA). Other than not meeting the inclusion criteria, there are no exclusion criteria.

**Activity 4:** For this analysis, the study cohort will consist of patients who: 1) have Type II diabetes, 2) are insured by Medicaid, and 3) are either part of a Health Home or meet criteria for Health Home enrollment, but are not enrolled in a Health Home. These criteria will be determined using only Medicaid claims data.

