Our sample will include Medicaid enrollees with diabetes who are seen at NYC-CDRN sites and in HHs (estimated 6,500-20,000) and a matched comparison group of Medicaid enrollees with diabetes who are part of the NYC-CDRN, but not HHs. We plan to develop a set of propensity score matched controls, based on a set of patient, practice, and market-level (zip-code) characteristics. We will use quasi-experimental methods to investigate the magnitude of the effects of the HHs program between 2010 and 2017. This secondary data analysis is referred to as **Activity 1** in this protocol. In addition, we will gather information regarding the patient experience of HHs through interviews (**Activity 2**). We will also utilize interviews with HH leaders and care managers from NYC HHs to further characterize these entities (**Activity 3**). Columbia University will participate in only **Activity 1**.

8/20/20 update: Apart from evaluating the impact of the NYS Medicaid HH program on the process and outcomes of care for low-income NYC residents with diabetes, compared to non-enrolled residents with similar conditions and utilization histories, we have received funding to extend this work to examine the impacts of the COVID-19 pandemic on this vulnerable population, a majority of which is Black or Latinx. We hypothesize that HH participation will reduce pandemic-related disruptions in access to health care and social services and improve health outcomes among patients with diabetes in NYC. Using a quasi-experimental difference-in-differences design, we will contrast access and utilization of health care and social services and health outcomes among HH enrollees and non-enrollees during a baseline period prior to the pandemic (CY2019) with each month of the pandemic time period (2020).

**Aim 4:** Using Medicaid claims data, we will estimate the impact of HH enrollment compared to usual care among Medicaid-insured patients with diabetes and other chronic conditions on access to health care and social services and COVID-19 and non-COVID-19 clinical outcomes, as well as racial/ethnic disparities in these outcomes, before and during the pandemic in NYC.

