The identification of individuals eligible for HHs is initiated by one of two processes: a NYS Department of Health (DOH) predictive algorithm utilizing Medicaid services data, which prioritizes individuals based on risk of future hospitalization; and community or “bottom up” referrals from healthcare providers, community-based care management providers, including harm reduction providers, and other agencies such as those who serve individuals re-entering the community from jail or prison. Enrollment in HHs has been slower than expected, and several challenges have been identified and are being addressed by the NYS DOH. These include inaccuracies in the lists of targeted individuals, challenges in the recruitment process, and individuals electing not to participate in the program.(16) The new program may put stress on already under-resourced facilities, by increasing the complexity of billing, the requirements around health information technology (HIT), the caseloads of facilities and case managers, and, in some cases, lowering reimbursement for care management services. Another significant change brought about by HHs is the expanded scope of health conditions of clients served by care management agencies that formerly provided case management for people living with HIV/AIDS, substance use disorders, or serious mental illness ([name], personal communication, March 9, 2015).

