**2) Health home indicators and patient co-morbidities**

Indicators available include whether the individual was enrolled in the HH program, the date of joining the program, the name/location of the HH, patient-level co-morbidities and chronic conditions (additional diagnoses).

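### Activity 1 groups patients by Health Home participation over the whole study period with no index date, which leaves the Aim 2 comparison open to selection on later events

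*Protocol*

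**What the plan says.** Protocol section 5b, Activity 1, item 3 sets the two groups. On treatment: "Subjects who have participated in the HH program will be the treatment group in this study". On how they are found: "Medicaid data contains a field that will identify those patients who were a part of this program during the study period". On comparison: "Our comparison group will consist of similar individuals who were not part of the HH program", chosen by propensity score matching. The opening of 5b admits patients who "are either part of a Health Home or meet criteria for Health Home enrollment, but are not enrolled in a Health Home", and item 2 says "subjects need to have been insured by Medicaid at some point during the years 2010-2016". None of these conditions is tied to a date.

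Other sections bear on the point:
- Section 5e, heading 2, lists "the date of joining the program" among the variables.
- Section 1 says "We will use quasi-experimental methods to investigate the magnitude of the effects of the HHs program between 2010 and 2017" and names no estimator and no start of follow-up.
- The Background says the program opened in NYC in two phases, in January and April 2012, and that enrolment was slower than planned. One of the two entry routes is a State algorithm "which prioritizes individuals based on risk of future hospitalization"; the other is community referral.
- For Activity 4, by contrast, section 1 identifies HH participants in 2019, before the 2020 outcome months.

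**The concern.** Joining was spread over years and partly driven by predicted hospitalization, so HH status read over the whole period is itself a result of follow-up. A patient counts as a comparator only if nothing later led to enrolment. Requiring this has two effects:
- The event-free time that future joiners contribute before joining is removed from the comparison group. For an event that ends the chance to join, this inflates the comparison rate and imitates a benefit.
- If admissions trigger recruitment, patients with admissions are drawn out of the comparison group. This lowers its admission rate and imitates harm.

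Propensity matching on patient, practice and zip-code characteristics balances what is measured at matching. It cannot balance whether a person enrols afterwards. If HH follow-up also began before joining, HH patients would carry time in which a terminal event was impossible by definition. Aim 2 (stroke, myocardial infarction, end-stage renal disease, amputation, preventable admissions) rests on this contrast.

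**Working it through.** The protocol gives no figure to reproduce here. The check takes the rule literally and then asks what it does when HHs have no effect.

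**1. The rule applied to the two extracts.** Sections 5d and 5f plan one data set for 2007-2014 and one for 2010-2017. A patient who joins in 2016 can be a comparator in the first and is treated in the second. The same 2010-2014 time changes group because of a later event.

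**2. Terminal event, true rate ratio 1.**

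Inputs from section 1: 6,500-20,000 HH patients among about 90,700, so shares of 6,500/90,700 = 7.2% and 20,000/90,700 = 22%.

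Assumptions, not in the protocol:
- T = 6 years (2012-2017).
- Constant joining rate λ = −ln(1 − share)/6, which is 0.0125 or 0.0414 per year.
- Event hazard h = 0.02, 0.05 or 0.10 per year, the same in and out of HHs.
- The event ends the chance of counting as a joiner.

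With a = λ + h, the mean times per cohort member are:
- not yet joined: m = (1 − e^(−aT))/a
- all follow-up: F = (1 − e^(−hT))/h
- follow-up of those who never join: P = h[(1 − e^(−aT))/a² − T·e^(−aT)/a] + T·e^(−aT)

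The three analyses give:
- (i) Any participation versus none, all time from 2012: (F − m)·P / [(F − P)·m]
- (ii) HH clock at joining, never-enrolled controls from 2012: P/m
- (iii) HH time from joining, all earlier time unexposed: [h(F − m)/(F − m)] / [hm/m] = 1

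Example with share 22% and h = 0.05: m = 4.618, F = 5.184, P = 4.097.
- (i) (0.565 × 4.097)/(1.087 × 4.618) = 0.46
- (ii) 4.097/4.618 = 0.89

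| Share | (i) | (ii) | (iii) |
|---|---|---|---|
| 7.2% | 0.49 | 0.96-0.97 | 1.00 |
| 22% | 0.46 | 0.88-0.89 | 1.00 |

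A simulation of the same set-up agreed: (i) 0.46-0.49; (ii) 0.96-0.97 and 0.89-0.90; (iii) 1.00-1.01. A second null simulation gave 0.41-0.49 for (i). For (ii) it gave 0.85-0.96 at HH shares of about 7-24%, and down to 0.75 at 35-41%.

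**3. Recurrent admissions, true rate ratio 1, HH clock at joining.** Assumed: 0.15 admissions per year, and a joining rate 1, 2 or 5 times higher in the six months after an admission. HH versus never-enrolled controls gave 0.99-1.06 at shares of 7.2% and 22%. HH versus not-yet-enrolled controls gave 0.99-1.01. Stronger assumptions (patients differing in frailty, shares up to 50%, a sixfold joining rate) took the never-enrolled comparison to 1.23. The 50% share exceeds what the protocol supports: 22% of 90,700, or 20,000/51,000 = 39% of the Activity 1 sample.

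**4. Repeatable measures (HbA1c, blood pressure, yearly process measures).** No time is guaranteed event-free, so the issue is pre-joining time counted as treated. With a true ratio of 0.80 and a fraction f of HH time before joining, the observed ratio is f × 1 + (1 − f) × 0.80. This gives 0.85, 0.90 and 0.95 for f = 0.25, 0.50 and 0.75.

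**The case against.** Section 5b says who is in the cohort; it need not state the exposure clock. Index dates and the handling of person-time are commonly left to a statistical analysis plan, which is not shown. Other features also point away from a naive analysis: the joining date is a listed variable, the data sets carry actual dates, and the extracts reach back before the 2012 launch. This much stands. A reader might infer that years before joining will be counted as treated, but no sentence says so, and the 0.4-0.5 ratio applies only if they are.

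A reader might also infer that comparators are people with a good future. The protocol does not support that either. Comparators must meet HH criteria, and the Background gives other reasons for non-enrolment: inaccurate lists, recruitment difficulties and refusal.

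The terminal-event model has limits too. Death and exit from Medicaid are not listed endpoints. A non-fatal stroke does not stop a patient from joining later, so those ratios carry over to a first event only if it removes the patient from the joiners.

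What the objection does not answer is the comparison group. Its definition is in the protocol, it is undated, and an analysis plan that followed it could not use patients who join later, even if it started HH time at joining.

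**Conclusion.** The point holds as a badly fixed group definition. It does not show that the estimates must be biased or that no HH effect could be read from them; that stronger conclusion would need a time zero the protocol does not give.

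Read as written, comparators are selected on events after any baseline. HH patients are too only if their clock starts before joining. Under a true null and the assumed rates, the size depends on that unstated choice:
- all time from 2012 counted: about 0.4-0.5 for terminal events, or first events that act like them
- HH clock at joining, controls never enrolled: about 0.85-0.97 at HH shares of about 7-24%
- admissions, HH clock at joining: about 1.0-1.1 at those shares, higher only under stronger assumptions
- repeatable measures: dilution rather than immortal time, if pre-joining time is counted as treated

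The possible bias therefore runs from negligible to severe, and its direction differs by endpoint. Dated exposure with not-yet-enrolled controls came out close to 1 throughout (0.99-1.03 across all admission runs).

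**What to change.** Rewrite section 5b, Activity 1, item 3 so that exposure is dated:
- HH exposure starts at the joining date already collected under section 5e.
- Each comparator gets a matched calendar index date, drawn from patients who on that date meet HH criteria, are enrolled in Medicaid and are not yet in an HH.
- Patients who join later are not excluded as comparators. They are censored, or switched to exposed, at joining.
- Eligibility and matching covariates are measured before the index date, and earlier time serves as baseline only.

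Monthly risk-set matching is one way to do this; another design that respects the same dates would also serve.

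The cost is protocol wording and somewhat more complex matching code, with no new data. Comparator follow-up is shortened when a comparator joins. Because joining partly follows risk, that censoring may be informative, so the approach to it must be stated, for example weighting for the probability of remaining un-enrolled.
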